6.1 Population characteristics

Subject enrollment and disposition will be summarized for the following via the enrolled cohort:

- Enrollment by site and overall
- Disposition (completed study (Y/N), etc.)
- Summary of all reasons for early termination
- Subject validity
- Visit accountability (enrolled subjects not screen failures)

The following demographic and baseline characteristics will be summarized descriptively for the Safety Cohort:

- Demography – Race, ethnicity, age, age groups (18-27, 28-33, >34, and also ≤ 45 , >45), weight [kg], height [cm], and body mass index [kg/m²]
- Medical History – Primary method of contraceptive used immediately prior to the Essure placement procedure, gravidity (both categorical and continuous), parity (both categorical and continuous), vaginal births (categorical only), cesarean births (categorical only), total abortions (categorical only), ectopic pregnancies (categorical only), days from last delivery/termination of pregnancy to NovaSure procedure, days from Essure procedure to NovaSure procedure, days from Essure confirmation test to NovaSure procedure, did Essure confirmation test show both micro-inserts in the

proper location (Y/N), did Essure confirmation test show both fallopian tubes occluded (Y/N), number of previous abdominal surgeries (continuous only), days from most recent abdominal surgery to NovaSure procedure,

- Pelvic exam (unremarkable/remarkable)

The following procedure data will be summarized descriptively for the Primary Effectiveness Cohort:

- NovaSure Procedure – Duration (minutes), anesthesia type (inhaled, IV, IM, oral, regional, local, other), uterine positions (Anteverted, Retroverted, Midpositional), cervical dilation required (Y/N), treatment time (seconds), power setting (continuous), was the ablation procedure interrupted during the treatment cycle (Y/N), was a restart of the endometrial ablation necessary (Y/N), was resistance encountered during withdrawal of the NovaSure device (Y/N), was an Essure micro-insert attached to the array upon removal (Y/N), was the endometrial ablation completed successfully (Y/N)
- Frequency summary of discharge medications
- Follow-up at 1 week, 1 year, 2 years and 3 years – has either Essure insert been expelled (Y/N), patient’s rating of comfort of wearing the micro-insert, patient’s rating of overall satisfaction with the micro-insert, patient’s rating of overall satisfaction with the treatment plan of Essure permanent birth control and confirmation test followed by NovaSure treatment

Protocol deviations will also be summarized by category of deviation for the enrolled cohort.

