1.5.3 Risk Analysis and Conclusions from Prior Reported Data

Clinical and commercial studies have evaluated over 250 patients who have had NovaSure EA while wearing the Essure micro-inserts. The adverse events reported in the clinical evaluations were similar to the adverse events experienced individually with each technology. All adverse events were expected, and, none of the adverse events were severe, confirming that it is safe to perform NovaSure EA on patients who are wearing the Essure micro-inserts. The most frequent adverse event that could be attributed to performing the two technologies together was the possibility of displacing or dislodging an implanted Essure micro-insert when performing NovaSure EA. The larger studies demonstrated that the Essure micro-inserts did not alter performance of NovaSure EA. The benefit of performing NovaSure EA in patients wearing the Essure micro-inserts outweighs the risk of the adverse events that are expected to occur. This clinical study will evaluate the ability of Essure micro-inserts to maintain contraception following NovaSure EA, providing further data to assess the risk-benefit ratio⁸.

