5.2 Withdrawal of subjects from study²¹

5.2.1 Withdrawal²² - amended

Subjects *must* be withdrawn from the study for the following reasons:

- At their own request or at the request of their legally acceptable representative
- At any time during the study and without giving reasons, a subject may decline to participate further. The subject will not suffer any disadvantage as a result.
- If, in the investigator's opinion, continuation of the study would be harmful to the subject's well-being

Subjects may be terminated from the study by the Investigator. Reasons for termination of a subject from the study may include, but are not limited to, the following:

- Subject does not retain device (e.g. due to removal of device, expulsion, salpingectomy or other utero-tubal surgeries)

¹⁹ Per Amendment 4 and 5

²⁰ Per Amendment 4

²¹ New section from sponsor template per Amendment 4

²² Withdrawal criteria adapted to suit a device meant for permanent wearing per Amendment 6.

- Death
- An adverse event (AE) preventing study participation
- Lost to follow-up and inability to contact the subject. Note that if a subject who is lost to follow-up is re-contacted, the subject will not be considered to have withdrawn from the study.

A subject who discontinues study participation prematurely for any reason is defined as a “dropout” if the subject has already undergone the NovaSure procedure.

A subject who, for any reason (e.g. failure to satisfy the selection criteria), terminates the study before the time point used for the definition of “dropout” (see above) is regarded a “screening failure”.

Any subject removed from the trial will remain under medical supervision until discharge or transfer is medically acceptable.

In all cases, the reason for withdrawal must be recorded in the case report form (CRF) and in the subject's medical records.

Details for the premature termination of the study as a whole (or components thereof [e.g. centers, treatment arms, dose steps]) are provided in Section 10 (Premature termination of the study).

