7.1.2.5 Notification of Other Relevant Events

The subject should be instructed at the beginning of the study to inform the site immediately if subject has had or is scheduled to have any surgery which may remove some or all of her reproductive organs (i.e. hysterectomy, salpingectomy or oophorectomy)²⁹.

The subject will also be instructed to contact the Investigator immediately if, at any time during the study, subject thinks she might be pregnant.

If a subject experiences a micro-insert expulsion or removal during or following the NovaSure procedure, subject will be followed for the duration of the adverse event, then terminated from the study.

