4.3 Handling of Missing Data

In order to achieve the goal of a well conducted clinical trial according to Good Clinical Practice (GCP), every effort will be made to collect all data. i.e., if a subject misses a

scheduled assessment, the site personnel will contact the subject and request her to come to the clinic for a visit. However, despite best efforts, it may be inevitable that missing or incomplete data are reported. Except as noted below, missing data will not be estimated or imputed.

General rules

When appropriate, the following rules will be implemented so as not to exclude subjects from statistical analyses due to missing or incomplete dates:

Table 1 - Imputation rules for missing adverse event start and stop dates

Scenario		
Start date	Stop date	Imputation rule
Partially Missing	Complete	
Imputation of start date:
 
A. If partial date has day and month missing: If the year is same as the year of the NovaSure EA procedure, then the day and month of the NovaSure EA procedure will be assigned to the missing fields If the year is prior to the year of the NovaSure EA procedure, then December 31 will be assigned to the missing fields. If the year is after the year of the NovaSure EA procedure, then January 01 will be assigned to the missing fields.
 
Note: if NovaSure EA procedure date is missing, then there is no need to impute the date as the AE is not treatment emergent.
 
B. If partial date has missing day only: If the month and year are same as the year and month of the NovaSure EA procedure, then the day of the NovaSure EA procedure will be assigned to the missing day.

		
If the month and year are before the year and month of the NovaSure EA procedure, then the last day of the month will be assigned to the missing day.
 
If the month and year are after the year and month of the NovaSure EA procedure, then the first day of the month will be assigned to the missing day.
 
If the imputed event start date (after A or B above) is after the event stop date, the start date will be imputed to be equal to the stop date.

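### By-visit expulsion rows in SAP 6.1 lose women terminated after an earlier expulsion, so the year 1–3 percentages understate cumulative expulsion

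*SAP*

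**What the plan says.** SAP 6.1 introduces a list with "The following procedure data will be summarized descriptively for the Primary Effectiveness Cohort". The list includes "Follow-up at 1 week, 1 year, 2 years and 3 years – has either Essure insert been expelled (Y/N"). Under SAP 6, a yes/no item becomes a frequency table of number and percentage. No denominator, cumulative or time-to-event rule is given for expulsion.

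On missing data, SAP 4.3 states: "Except as noted below, missing data will not be estimated or imputed". The exceptions are adverse event start and stop dates. SAP 4.2 keeps dropouts in every analysis set for which they qualify, but does not say what status they have at visits they never reach.

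On what follows an expulsion, the protocol has two texts:
- Section 7.1.2.5, on a woman with an expulsion or removal: "subject will be followed for the duration of the adverse event, then terminated from the study".
- Section 5.2.1: "Subjects may be terminated from the study by the Investigator", with one listed reason being "Subject does not retain device (e.g. due to removal of device, expulsion, salpingectomy or other utero-tubal surgeries").

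Protocol 1.5.3 says the most frequent adverse event attributable to combining the two technologies was "the possibility of displacing or dislodging an implanted Essure micro-insert when performing NovaSure EA".

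**The concern.** The wording of the item reads as a cumulative status: has an insert come out at any time so far. As written, the table cannot deliver that. The event being counted is itself the reason a woman leaves follow-up, so a Yes does not persist into later rows. An expulsion that is reported and closed between two annual calls may appear in no row.

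A low 3-year row could then be read as insert retention through 3 years, when part of it comes from the termination rule. Monitoring complications of NovaSure with Essure in place is one of the study's two objectives, and this item is the only specified output that places expulsion on the time axis since NovaSure.

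**Working it through.** The documents state no expected expulsion rate, so there is no planned figure to reproduce. The check has two parts.

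**1. The written rules applied to three records.** Assume termination under Protocol 7.1.2.5 and no carry-forward.
- A: insert withdrawn with the array on Day 0; event ends on day 3; terminated.
- B: expulsion reported at month 5; event closed and woman terminated at month 6.
- C: expulsion first disclosed at the 1-year call; terminated before the 2-year call.

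| | 1 week | 1 year | 2 years | 3 years |
|---|---|---|---|---|
| Yes in the by-visit row | 0 | 1 (C) | 0 | 0 |
| Women with a loss so far | 1 (A) | 3 | 3 | 3 |

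Record A would appear in the separate SAP 6.1 procedure item on whether an insert was attached to the array, but in none of the four expulsion rows.

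**2. By-visit percentage against cumulative percentage.** Assumed inputs, none of them set by the documents:
- p0, the proportion lost on Day 0. The only count available is 2 of 118 = 1.69%, from a retrospective case review in Protocol 1.5.2.
- h, the proportion of women still retaining inserts who expel one in each later year: 0.5% or 1%.
- q, the share of newly expelled women who still answer at their next scheduled contact: 0 to 1.
- Women expelled in an earlier interval no longer answer, and there is no other loss to follow-up.

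Cumulative by year y: 1 − (1 − p0)(1 − h)^y.

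By-visit row at any of years 1–3: qh / [(1 − h) + qh]. The number still at risk cancels, so this row does not depend on p0: Day 0 losses leave no trace in it.

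With p0 = 1.69% and h = 0.5% at year 3:
- Cumulative: 1 − 0.98305 × 0.995³ = 1 − 0.9684 = 3.16%.
- Row, q = 1: 0.005 / 1 = 0.5%.
- Row, q = 0.5: 0.0025 / 0.9975 = 0.25%.
- Row, q = 0: 0%.

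| p0 | h | Cumulative, years 1 / 2 / 3 | Row in each year, q = 0 / 0.5 / 1 |
|---|---|---|---|
| 0% | 0.5% | 0.50 / 1.00 / 1.49% | 0 / 0.25 / 0.50% |
| 1.69% | 0% | 1.69 / 1.69 / 1.69% | 0 / 0 / 0% |
| 1.69% | 0.5% | 2.19 / 2.68 / 3.16% | 0 / 0.25 / 0.50% |
| 1.69% | 1% | 2.68 / 3.65 / 4.61% | 0 / 0.50 / 1.00% |

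The direction is the same in every line. The two figures agree only at year 1, and only when nothing was lost on Day 0 and every newly expelled woman answers (first line, q = 1).

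**The case against.** The strongest reply is that the study does not lose these events. SAP 6.3.1 tabulates events and subjects for expulsion, migration or unintentional removal as an adverse event of special interest. SAP 6.3 puts this on the Safety Cohort, which by definition contains the effectiveness cohort. SAP 6.3 also counts device removals, and SAP 6.1 reports all reasons for early termination and, on the same cohort as the expulsion item, whether an insert was attached to the array. This stands: the overall count survives, provided each loss is recorded as an adverse event. What these outputs lack is time since NovaSure. The special-interest table has no breakdown by year and pools expulsion with migration and unintentional removal, the removal summary is timed from the last insert procedure, and the array item covers Day 0 only.

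Three stronger readings are tempting and not supported.
- A reader might infer that women are always terminated before their next visit, which would force the later rows to zero. Neither section says so. Section 7.1.2.5 ties termination to the end of an event of unstated length, and 5.2.1 makes it optional. Contacts after week 1 are annual, and the matters women are told to report at once are reproductive surgery and suspected pregnancy, not expulsion. An expulsion first disclosed at an annual call is a Yes there.
- A reader might take 2 of 118 as a forecast, about 3.7 women in 220. Most of those women had ablation without waiting for the 90-day test, whereas this study requires a successful confirmation test. In both cases a second device was placed. The figure serves only to illustrate.
- A reader might count intentional removals as missed Yes answers. The item asks about expulsion only.

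It is also fair to say that the CRFs are not attached, so whether the question is asked cumulatively or since last contact cannot be seen. Either way, a woman who has left cannot answer it.

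**Conclusion.** The point holds as a reporting defect. With termination after expulsion and no carry-forward, the year 1–3 rows show only losses disclosed by women still in follow-up, and lie below cumulative expulsion whenever earlier losses have led to termination. The rows need not be zero, and the size of the gap cannot be fixed from the documents. Under the assumed rates above it runs from nothing (year 1, no Day 0 loss, everyone answering) to 4.6 percentage points (year 3, p0 = 1.69%, h = 1%, q = 0). It would be smaller if investigators used the discretion in Protocol 5.2.1 to keep such women in follow-up.

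The output is descriptive and carries no hypothesis. It is not an input to the pregnancy-rate calculation, the 1-year success rule or the stated power. The change is still worth making, because no other specified output shows when after NovaSure expulsions occurred.

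**What to change.** In SAP 6.1, replace or supplement the by-visit item with the cumulative number and percentage of Primary Effectiveness Cohort women with a first expulsion or unintentional loss since NovaSure, by 1 week and by 1, 2 and 3 years. Specifically:
- Include an insert withdrawn with the array.
- Keep a woman counted after she is terminated.
- Give a cumulative-incidence estimate so that women who leave early for other reasons are handled. Kaplan-Meier is already planned for pregnancy in SAP 6.2.1.
- Report intentional removal separately.
- State the denominator.
- Cross-reference the special-interest and removal tables in SAP 6.3 and 6.3.1, so that differing counts can be traced.
- Flag losses with a wholly missing start date, because SAP 4.3 would place them on the procedure date.

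Protocol 5.2.1 (optional termination) and 7.1.2.5 (termination once the event ends) must be reconciled, since the by-visit denominators depend on which was followed. The table change requires neither rule to be altered.

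The cost is one table specification and a little programming, drawing on procedure, adverse event, removal and follow-up data that the SAP already summarises. The downside for the sponsor is a slightly less favourable expulsion figure.

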6.2 Efficacy

6.2.1 Primary Efficacy Analysis

The primary effectiveness endpoint of this study is the 1-year and 3-year pregnancy rates. The rates will be calculated as done in prior Essure studies, as described below.

Each woman-month of follow-up represents a “Bernoulli trial” of the Essure device. A woman contributes as many women-months as her participation in the post-approval study. Upon observing f failures (pregnancies) in w women-months, the posterior distribution of the monthly failure rate, r , is calculated as:

$$r = \text{beta}(a+f, b+w-f)$$

where a and $b = 0.5$, representing a non-informative prior distribution. The upper Bayesian credible interval of r is easily calculated from the inverse beta function. A 1-year failure rate can be calculated as:

$$1\text{-year rate} = 1 - (1 - r)^{12}$$

The 1-year rate will be calculated when all participating women have reached at least 1 year of follow-up.

As an additional related calculation, the 3-year failure rate will be determined as:

$$3\text{-year rate} = 1 - (1 - r)^{36}$$

- For example, if there are 0 failures in $200 \times 12 = 2,400$ women-months, the posterior distribution of the monthly failure rate is $\text{beta}(0.5, 0.5 + 2400)$. The upper Bayesian credible interval is (in Excel) $\text{betainv}(.975, 0.5, 0.5 + 2400) = 0.00105$. The upper 95% credible interval for the 1-year rate is $1 - (1 - 0.00105)^{12} = 0.0125$ or 1.25%. This value meets the pre-determined study success threshold of 2.1% for the 1-year rate. 2.1% refers to the Upper Confidence Limit of the Adiana 1-year failure rate and 2.8% refers to the Upper Confidence Limit of the Adiana 3-year failure rate. (from Table 5: Contraceptive Failure Rates, Adiana Permanent Contraception Instructions For Use, AW-03216-001 Rev. 003);

The analysis population is the Primary Effectiveness Cohort.

The primary objective of the PAS is to evaluate the contraceptive failure rate of Essure when NovaSure EA is performed following a successful Essure Confirmation Test and to demonstrate that the failure rate is reasonably low (see details below). Consistent with prior Essure clinical studies, a Bayesian approach will be used. The study will be considered a success if the posterior probability (PPr) that the observed failure rate at 1 year (rate1y) is $< 2.1\%$ is at least 97.5%, i.e.:

$$\text{PPr}(\text{rate1y} < 0.021) > 0.975 *$$

* i.e., a Type 1 error rate of 5%

This equation provides the posterior probability that the one-year pregnancy rate is less than 2.1% given trial data is at least 97.5%. If the posterior probability that the 1-year rate is < 0.021 exceeds 97.5%, we have shown with a high degree of confidence that the rate is at least as good as that which FDA has found acceptable for Adiana Permanent Contraceptive (PMA P070022).

For the three-year rate, the same procedure is followed with the only exception that the threshold value is 2.8%, rather than the 2.1% specified for the one-year rate.

As a supportive analysis, the pregnancy rate will be also calculated using Kaplan-Meier method.

Assumptions

The following assumptions were used to calculate the PAS sample size and power for the 1- and 3-year hypothesis:

- Participants in this PAS are women who have undergone the Essure procedure followed by a successful Essure Confirmation Test showing satisfactory micro-insert location and bilateral tubal occlusion;
- Contraceptive failure rates after Essure are very low (no pregnancies identified in References 4 and 5 (two retrospective studies) in the clinical study protocol)) for the PAS population as demonstrated by prior clinical studies;
- For the purposes of power calculations, the one-year pregnancy rate is modeled as $r = \text{beta}(0.5+a, 0.5+b)$, where $\text{beta}(0.5,0.5)$ is a non-informative prior and $a=0$, $b=600$, roughly the size of the Essure Phase II and Pivotal clinical trial relying cohorts in the Essure premarket studies;
- Multiple clinical trials are simulated with the underlying pregnancy rate of r ;
- The one-sided upper Bayesian credible interval of the observed one-year failure rate amongst $n=200$ is calculated in 5000 simulated clinical trials using an underlying pregnancy rate of r ;
- Power for the 1-year hypothesis is the probability (based on 5000 simulated clinical trials) that the Upper Credible Interval of the 1-year rate is $<2.1\%$, where 2.1% is the Upper Confidence Limit of the Adiana 1-year failure rate (from Table 5 in the clinical study protocol: Contraceptive Failure Rates, Adiana Permanent Contraception Instructions For Use, AW-03216-001 Rev. 003);
- Power for the 3-year hypothesis is the probability that the Upper Credible Interval of the 3-year rate is $<2.8\%$, the Upper Confidence Limit of the Adiana 3-year failure rate (Table 5: Contraceptive Failure Rates, Adiana Permanent Contraception Instructions For Use, AW-03216-001 Rev. 003).

Given the assumed underlying failure rate for a successful Essure procedure followed by a confirmatory Essure Confirmation Test, a study of $n=200$ women has an 86% chance of showing that the Upper Credible Interval of the 1-year failure rate will be $<2.1\%$. The table below shows detailed results.

Expected number of failures at 1 year	Probability	2-sided upper credible interval
--	--------------------	--

0	0.861	0.012
1	0.112	0.023
2	0.020	0.031
3	0.006	0.039
4	0.002	0.047
5	0.0004	0.054

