- Power for the 3-year hypothesis is the probability that the Upper Confidence Limit of the 3-year rate is $<2.8\%$, the Upper Confidence Limit of the Adiana 3-year failure rate (Table 5: Contraceptive Failure Rates, Adiana Permanent Contraception Instructions For Use, AW-03216-001 Rev. 003).

Given the assumed underlying failure rate for a successful Essure procedure followed by a confirmatory Essure Confirmation Test, a study of $n=200$ women has an 86% chance of showing that the Upper Confidence Limit of the 1-year failure rate will be $<2.1\%$. The table below shows detailed results.

| Expected number of failures at 1 year | Probability | 2-sided upper credible interval |
|---------------------------------------|-------------|---------------------------------|
| 0 | 0.861 | 0.012 |
| 1 | 0.112 | 0.023 |
| 2 | 0.020 | 0.031 |
| 3 | 0.006 | 0.039 |
| 4 | 0.002 | 0.047 |
| 5 | 0.0004 | 0.054 |

9. Data handling and quality assurance ⁴⁹

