End of study

The primary outcome will be collected after last patient - last visit (LPLV). The end of the study as a whole will be the date when the clean data base is available.

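### The stated 86% power assumes 12 months per woman, but the written 1-year rule counts every month of participation and so passes with roughly 3 to 7 pregnancies, not 0

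*SAP*

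**What the plan says.** SAP 6.2.1 and Protocol 8.4.1 treat each woman-month as a Bernoulli trial with one monthly failure rate r. From f failures in w woman-months and a beta(0.5, 0.5) prior, the posterior of r is beta(0.5+f, 0.5+w−f). The 1-year rate is 1−(1−r)^12 and the 3-year rate is 1−(1−r)^36. The exposure rule is "A woman contributes as many women-months as her participation in the post-approval study". Follow-up is 3 years (SAP 3). On timing, SAP 6.2.1 adds: "The 1-year rate will be calculated when all participating women have reached at least 1 year of follow-up".

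The illustration in the same section reads "if there are 0 failures in $200 \times 12 = 2,400$ women-months" and reaches an upper limit of 1.25%. The power statement says that a study of 200 "women has an 86% chance of showing that the Upper Credible Interval of the 1-year failure rate will be" below 2.1%; Protocol 8.6 gives the same 86%. The accompanying table counts failures at 1 year and lists 0 failures with probability 0.861 and limit 0.012, and 1 failure with limit 0.023.

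The SAP declares success if the posterior probability of a 1-year rate below 2.1% exceeds 97.5%. It then says: "For the three-year rate, the same procedure is followed with the only exception that the threshold value is 2.8" per cent. The power assumptions open with "The following assumptions were used to calculate the PAS sample size and power for the 1- and 3-year hypothesis", but no 3-year power follows.

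**The concern.** The rule and the figures that describe it use different denominators. The rule accumulates up to 36 months per woman. The example, the table and the 86% stop at 12. A reader who takes the table at its word concludes that a single pregnancy fails the 1-year goal; a programmer who follows the rule will let several through.

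The pooled version also changes what the 1-year goal tests. On the same data, both goals become limits on one parameter: r below 1−0.979^(1/12) = 0.00177 at 1 year, and r below 1−0.972^(1/36) = 0.00079 at 3 years. The 1-year goal is then met whenever the 3-year goal is, and it says nothing separate about year 1. That is acceptable only if monthly risk is constant over three years, which the plan does not justify. The explicit success sentence names only the 1-year rate.

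**Working it through.** **Inputs.** Prior, formulas, 97.5% criterion, thresholds 2.1% and 2.8%, and n=200: SAP 6.2.1. True 1-year rate for power: beta(0.5, 600.5), from a=0, b=600 in SAP 6.2.1. Minimum enrolment 220: SAP 3. Enrolment NOV 2012 to DEC 2017: Protocol 15. Dropout: not given, so assumed.

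**Formulas.** Upper limit = 1−(1−BETAINV(0.975; 0.5+f, 0.5+w−f))^12, or ^36 for 3 years. Pass mark = largest f whose limit is below the threshold. Power: draw p from beta(0.5, 600.5), set r = 1−(1−p)^(1/12), and take the probability that a binomial(w, r) count does not exceed the pass mark.

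**The plan's own figures.** With w = 2,400, the limits for f = 0 to 5 are 0.0125, 0.0231, 0.0316, 0.0393, 0.0465 and 0.0534. The table has 0.012, 0.023, 0.031, 0.039, 0.047 and 0.054, so agreement is within about 0.001. Only f = 0 is below 0.021. The chance of 0 failures in 200 women is 0.866, against the stated 0.861. Allowing 1 failure, as the Protocol's 95% criterion would on 2,400 months, gives 0.974 and does not reproduce 86%. The 86% therefore belongs to 12 months per woman and a pass mark of 0.

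**Exposure under the written rule.** Assume uniform accrual over 61 months and no dropout. When the last woman reaches 1 year, those enrolled in the first 37 months have 36 months each, and the rest average 24: (37×36 + 24×24)/61 = 31.28 months. That gives 200×31.28 = 6,256 or 220×31.28 = 6,881 months. After the last visit it is 200×36 = 7,200 or 220×36 = 7,920. With an assumed exponential dropout of 15% per year, 200 women give 5,050 months at the 1-year time and 5,698 after the last visit. With 10%, 220 women give 5,977 at the 1-year time.

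| w (months) | 1-year pass mark | 1-year power | 3-year pass mark | 3-year power |
|---|---|---|---|---|
| 2,400 | 0 | 86.6% | none | 0 |
| 5,050 | 3 | 99.0% | 0 | 77% |
| 5,698 | 4 | 99.5% | 0 | 75% |
| 5,977 | 4 | 99.4% | 1 | 91% |
| 6,256 | 5 | 99.7% | 1 | 90% |
| 6,881 | 5 | 99.6% | 1 | 89% |
| 7,200 | 6 | 99.8% | 1 | 88% |
| 7,920 | 7 | 99.8% | 1 | 87% |

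Women who become pregnant are not censored here. Censoring them at month 6 lowers the 1-year mark from 5 to 4 at 6,256 months and from 7 to 6 at 7,920.

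**3-year goal.** With 0 pregnancies in 2,400 months the 3-year limit is 3.70%, above 2.8%. The smallest w that passes is 3,184 for f = 0, 5,926 for f = 1 and 8,135 for f = 2. The example's denominator cannot serve both goals.

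**What constant risk carries.** Take 5 first-year pregnancies among 220 women (5/220 = 2.3%) and none later. On 6,881 pooled months the 1-year limit is 1.89% (pass). On the first 12 months, 220×12 = 2,640, it is 4.86% (fail). The pooled 3-year limit is 5.57% (fail).

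**The case against.** Pooling is stated openly, and the model is visible: a Bernoulli trial per month with a single r, raised to powers 12 and 36, is a constant-risk model. This stands. The assumption is not hidden; only its justification is missing.

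The endpoint wording, the example and the table heading all point to 1 year, so 12 months may have been intended. This is possible, but an example does not cap a rule, and the rule has no cap.

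A reader might infer that the two timing statements conflict, since the 1-year rate is calculated once every woman has at least a year, while the primary outcome is collected after the last visit. The documents do not support that. The outcome has a 1-year and a 3-year part, at least a year is a minimum, and the two statements can be read together.

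A pass mark that moves with exposure is also normal for a posterior-probability rule and is not a defect in itself. The defect is that the published power and table describe another denominator.

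Finally, the stated power errs low, so the 1-year goal is not underpowered. A first-year cluster would also miss the 3-year goal and would show in the supportive Kaplan-Meier analysis. All of this is right, and it limits the harm. It does not make 86% the power of the written rule.

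**Conclusion.** The point holds. The 86% power and its table belong to 12 months per woman with 0 pregnancies allowed; the rule as written has no such limit. Under the SAP's 97.5% criterion and pooled exposure of about 5,050 to 7,920 months, up to 3 to 7 pregnancies pass, with power of about 99 to 99.8%. For the 3-year goal, 1 pregnancy is allowed from about 5,926 months (power about 87 to 91%). At 5,050 to 5,698 months none is allowed (about 75 to 77%), and on 2,400 months the goal cannot be met.

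These ranges rest on uniform accrual over the projected dates and on assumed dropout of 0 to 15% per year. The top of the range needs 220 women with no attrition for 36 months.

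A reader might go further and infer that the pooled rule is invalid or that it inflates false success. The documents do not show that risk is concentrated in year 1, and pooling is sound if risk is constant. The 5-pregnancy case shows what the assumption carries; it is not a forecast.

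**What to change.** State in SAP 6.2.1 and Protocol 8.4.1 which months and which pregnancies feed the 1-year rate and which feed the 3-year rate.

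If pooling is kept, restate the worked example, the power and the table on the pooled denominator with the assumed dropout. Give the 3-year power. State the constant-risk assumption. Prespecify the 1-year rate limited to the first 12 months as a sensitivity analysis, reported alongside the success conclusion. The decisive calculation does not change.

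If 12 months was always intended, write it into the rule. This is the more delicate route. SAP version 1.1 is dated 15Dec2020, final follow-up was expected in JAN 2021, and pregnancies appear in the interim reports. The change should be dated, with disclosure of what was already known. It also widens the 1-year interval: 0 pregnancies gives 1.25% on 2,400 months, against 0.44% on 6,881.

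The cost is a few sentences, a recomputed table, one extra analysis and a rule for the pregnancy event date. The Kaplan-Meier analysis needs that rule anyway, because the SAP's date imputation covers adverse events only.
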